### **Data Management**

The sponsor is responsible for the data management of this study including quality checking of the data (Section 11.1).

### **Study Monitoring**

The investigator must allow study-related monitoring, IRB/EC review, audits, and inspections from relevant health regulatory authorities, and provide direct access to source data documents (Section 12.1, Section 12.2, and Section 13).

The study monitors will perform ongoing source data review to verify that data recorded in the CRF by authorized site personnel are accurate, complete, and verifiable from source documents, that the safety and rights of patients are being protected, and that the study is being conducted in accordance with the current approved protocol version and any other study agreements, ICH GCP, and all applicable regulatory requirements (Section 12.1).

All patient data collected during the study will be recorded on paper or eCRF unless the data are transmitted to the sponsor or designee electronically (eg, laboratory data). The investigator is responsible for affirming that data entries in the CRF are accurate and correct by electronically signing a declaration that accompanies each set of patient final CRF (Section 12.3, Section 17.1).

### **Study Documentation**

The investigator must maintain accurate documentation (source data) that supports the information entered in the CRF (Section 12.2).

The investigator will retain all records and documents, including signed ICFs, pertaining to the conduct of this study for at least 15 years after study completion, unless local regulations or institutional policies require a longer retention period. No records may be destroyed during the retention period without the written approval of the sponsor. No records may be transferred to another location or party without written notification to the sponsor (Section 17.2).

## **19. CONFIDENTIALITY**

Confidentiality of information is provided as a separate agreement.

## **20. FINANCING AND INSURANCE**

Financing and insurance information is provided as a separate agreement.

## **21. PUBLICATION POLICY**

The publication policy is provided as a separate agreement.

## LIST OF ABBREVIATIONS AND DEFINITION OF TERMS

AA	Adjudicated Arthropathy
ADA	Anti-drug antibody
AE	Adverse event
AESI	Adverse event of special interest
ALT	Alanine aminotransferase
AST	Aspartate aminotransferase
CI	Confidence Interval
DA	Destructive Arthropathy
ECG	Electrocardiogram
eCRF	Electronic case report form
EDC	Electronic data capture
EQ-5D	EuroQol Group Questionnaire
FAS	Full analysis set
FDA	Food and Drug Administration
GCP	Good Clinical Practice
HbA1c	Hemoglobin A1c
ICF	Informed consent form
ICH	International Conference on Harmonization
IVRS	Interactive Voice Response System
JR	Joint replacement
K-L	Kellgren-Lawrence
LS	Least Squares
MedDRA ®	Medical Dictionary for Regulatory Activities
MMRM	Mixed-effect model for repeated measures
MRI	Magnetic resonance imaging
NGF	Nerve growth factor
NRS	Numeric Rating Scale
NSAIDs	Nonsteroidal anti-inflammatory drugs
OA	Osteoarthritis
OMERCAT- OARSI	Osteoarthritis Research Society International Standing Committee for Clinical Trials Response Criteria Initiative and The Outcome Measure in Rheumatology
PCSV	Potentially clinically significant value
PK	Pharmacokinetic
PPS	Per protocol set
PT	Preferred term

Q4	Every 4 (weeks)
Q8	Every 8 (weeks)
RBC	Red blood cell
Regeneron	Regeneron Pharmaceuticals, Inc.
RPOA	Rapidly Progressive Osteo-Arthritis
SAE	Serious adverse event
SAF	Safety analysis set
SAP	Statistical analysis plan
SAS	Statistical Analysis Software
SC	Subcutaneous
SD	Standard deviation
SF-36	Short Form (36) Health Survey
SOC	System organ class
TEAE	Treatment-emergent adverse event
TJR	Total joint replacement
ULN	Upper limit of normal
WBC	White blood cell
WOMAC	Western Ontario and McMaster Osteoarthritis Index

## **1. OVERVIEW**

The purpose of the statistical analysis plan (SAP) is to ensure the credibility of the study results by pre-specifying the statistical approaches for the analysis of study data prior to database lock. The SAP is intended to be a comprehensive and detailed description of the strategy and statistical methods to be used in the analysis of data for R475-OA-1688 study.

This plan may be revised during the study to accommodate protocol amendments and/or to make changes to adapt to unexpected issues in study execution and/or data that affect planned analyses. These revisions will be based on blinded review of the study and data, and a final plan will be issued prior to data lock and before code breaking.

### **1.1. Background/Rationale**

This randomized, double-blind, placebo- and NSAID-controlled study is designed to evaluate the efficacy and safety of fasinumab in patients with OA of the knee or hip who have a history of inadequate pain relief from acetaminophen/paracetamol and a history of intolerance to or inadequate pain relief from opioids (or are unwilling to and/or lack access to take opioids) for OA pain management. This study will compare the efficacy and safety of fasinumab to placebo and to a pooled NSAID group of celecoxib or diclofenac, which are members of the class of NSAID medications commonly used for moderate-to-severe pain due to OA.

The target study population was chosen because they currently have unmet medical needs with respect to incomplete pain control, despite the availability of NSAIDs i.e. they have failed or are intolerant to opioids and have failed acetaminophen/paracetamol and thus provides equipoise with regards to randomization of patients to fasinumab or placebo. Patients were also required to be on a stable dose of NSAID, defined as oral NSAID use at regularly prescribed doses for approximately 4 days per week over the last 4 weeks prior to the start of the screening period.

This study will provide efficacy and safety data for OA patients exposed for up to 24 weeks to fasinumab, a pooled NSAID comparator group (celecoxib or diclofenac), or placebo.

### **1.2. Study Objectives**

#### **1.2.1. Primary Objectives**

The primary objective of the study is to evaluate the efficacy of fasinumab compared to placebo, when administered for up to 24 weeks in patients with pain due to OA of the knee or hip.

#### **1.2.2. Secondary Objectives**

The secondary objectives of the study are:

- To evaluate the efficacy of fasinumab compared to NSAIDs, when administered for up to 24 weeks in patients with pain due to OA of the knee or hip
- To assess the safety and tolerability of fasinumab compared to placebo and compared to NSAIDs, when administered for up to 24 weeks in patients with pain due to OA of the knee or hip

- To characterize the concentrations of fasinumab over time when administered for up to 24 weeks in patients with pain due to OA of the knee or hip
- To evaluate the immunogenicity of fasinumab administered for up to 24 weeks in patients with pain due to OA of the knee or hip

### **1.2.3. Exploratory Objectives**

- To evaluate patient-reported outcome measures in patients with pain due to OA of the knee or hip treated for up to 24 weeks with fasinumab compared to placebo and compared to NSAIDs
- To evaluate the use of rescue medication in patients with pain due to OA of the knee or hip treated for up to 24 weeks with fasinumab compared to placebo and compared to NSAIDs

### **1.2.4. Modifications from the Statistical Section in the Final Protocol**

This SAP is based on Protocol R475-OA-1688 Amendment 4. The following were modified or were not specified in the protocol but are being clarified/added in this SAP:

- The Per-protocol set (PPS) was updated to exclude patients with relevant protocol deviations rather than major protocol deviations as stated in the protocol since not all major/important protocol deviations will lead to removal of patients from the PPS.
- The Urgent Safety Measure Set (USMS) was explicitly defined in this SAP since the protocol intimates that USM patients will not be included as part of the full analysis set (FAS).
- The Neutralizing Anti-Body (Nab) Set was included to support the ADA analysis that is planned to be performed.
- Subgroup analyses for the change from baseline in WOMAC pain subscale and physical function subscale scores at week 24 by flare status. Flare patients are defined as patients who experience a  $\geq 1$  point increase in WOMAC pain scores from the Screening to the Baseline Visit.
- Analyses for the percentage of patients who had improvements of  $\geq 50\%$  and  $\geq 70\%$  in the WOMAC pain subscale scores at week 24
- Analyses for the percentage of patients who had improvements of  $\geq 30\%$ ,  $\geq 50\%$  and  $\geq 70\%$  in the WOMAC physical function subscale scores at week 24
- Analyses for the percentage of patients who met the OMERACT-OARSI criterion at week 24. The OMERACT-OARSI criterion are described in Appendix Section 10.5 of this SAP.
- Analyses for additional exploratory endpoints of change in WOMAC pain and physical function subscale scores from baseline to the average score across Weeks 12, 16, 20 and 24.

### **1.2.5. Revision History for SAP Amendments**

[figure not shown]
None.

## 2. INVESTIGATION PLAN

### 2.1. Study Design and Randomization

This study is a randomized, double-blind, placebo- and NSAID-controlled study designed to evaluate the efficacy and safety of fasinumab in patients with OA of the knee or hip who have a history of inadequate pain relief with acetaminophen/paracetamol and a history of intolerance to or inadequate pain relief with opioids (or are unwilling to take opioids or have lack of access to opioids). The study consists of a screening period of up to 30 days, a 7 to 10 day pre-randomization/washout period (7 days with a +3 day window), a 24-week treatment period (with the last Q4W dose of study drug administered at week 20), a 20-week follow-up period, and a final phone call approximately 52 weeks after the last SC dose of study drug (Figure 1).

**Figure 1: Study Flow Diagram**

EOS- End of study

Patients will be randomized on day 1 (baseline) to one of the following treatment groups:

- Fasinumab 1 mg SC Q4W and NSAID-matching placebo oral, twice daily
- Fasinumab-matching placebo SC Q4W and diclofenac 75 mg oral, twice daily and NSAID matching placebo oral once daily
- Fasinumab-matching placebo SC Q4W, celecoxib 200 mg oral once daily, and NSAID-matching placebo oral once daily
- Fasinumab-matching placebo SC Q4W and NSAID-matching placebo oral, twice daily

Randomization will be stratified according to the affected index joint (hip or knee), the K-L score (2 to 3, or 4) at the screening visit, and geographical region (Asia/Pacific, Europe and North America).

### 2.2. Sample Size and Power Considerations

Assuming a 2-sided alpha level of 0.05 and a 20% dropout rate up to week 24, an enrollment of 600 patients in the fasinumab 1 mg Q4W group and 300 patients in the placebo group will provide at least 99% power to detect an effect size of 0.46 in the WOMAC pain and physical function subscale scores (i.e., absolute treatment difference of 1.1 between fasinumab and placebo with a SD of 2.4). The assumed treatment difference and standard deviation (SD) are based on results from study R475-PN-1227. The sample size will provide 99% power to detect

an effect size of 0.36 in PGA (i.e., absolute treatment difference of 0.4 with a SD of 1.1, R475-PN-1227).

Assuming a 2-sided alpha level 0.05 and a 20% dropout rate up to week 24, an enrollment of 600 patients in the fasinumab 1 mg Q4W group and the pooled NSAIDs group will provide approximately 92% power to detect an effect size of 0.22 in the WOMAC pain subscale (i.e., absolute treatment difference of 0.51 with a SD of 2.3, [Schnitzer 2015]). The sample size will provide 95% power to detect an effect size of 0.24 in WOMAC physical function subscale (i.e., absolute treatment difference of 0.50 with a SD of 2.1, [Schnitzer 2015]), and 79% power to detect an effect size of 0.18 in PGA (i.e., absolute treatment difference of 0.18 with a SD of 1.0 [Ekman 2014]).

The sample size has been revised from 2700 patients in the previous amendments to approximately 1620 patients in amendment 4 due to the discontinuation of fasinumab 3 mg Q4W and 6 mg Q8W dose regimens. There will be approximately 600 patients randomized to the fasinumab 1 mg SC Q4W group, 300 patients randomized to the each of the NSAID groups, and 300 patients randomized to the placebo group (a total of 1500 patients). In addition, approximately 60 patients each were enrolled in the fasinumab 3 mg SC Q4W and 6 mg SC Q8W groups under earlier versions of the protocol before dosing was discontinued in these treatment groups.

### **2.3. Study Plan**

Study assessments and procedures are presented by study period and visit in Section [10.2](#), [Table 2](#).

### 3. ANALYSIS POPULATIONS

In accordance with guidance from the International Conference of Harmonization of Technical Requirements for Registration of Pharmaceuticals for Human Use (ICH) guideline ICH E9 Statistical Principles for Clinical Trials (ICH, 1998), the following populations of analysis will be used for all statistical analysis:

#### 3.1. The Full Analysis Set (FAS)

The full analysis set (FAS) includes all randomized patients excluding patients affected by the urgent safety measure (i.e. patients randomized to the 3 mg Q4W or 6 mg Q8W doses) and is based on the treatment allocated (as randomized). Efficacy endpoints will be analyzed using the FAS including patients randomized to fasinumab 1 mg Q4W, NSAIDs, and placebo.

Efficacy data from patients randomized to fasinumab 3 mg Q4W or 6 mg Q8W will not be included in the analysis, but will be summarized descriptively in separate tables.

#### 3.2. The Modified Full Analysis Set (mFAS)

The modified full analysis set (mFAS) includes all randomized patients in the FAS but excludes patients from four sites (██████████) for which there were potential concerns regarding data quality. The co-primary endpoints and selected secondary endpoints may be evaluated in the mFAS as a sensitivity analysis.

#### 3.3. The Per Protocol Set (PPS)

The per protocol set (PPS) will include all randomized patients from the FAS who complete the 24-week treatment period and who do not have to be excluded due to relevant protocol deviations. The PPS will be used to perform sensitivity analyses for the primary and selected secondary endpoints.

Section 10.4 contains the list of protocol violations which lead to exclusion from the PPS and corresponding PDID.

#### 3.4. The Safety Analysis Set (SAF)

The safety analysis set (SAF) includes all randomized patients from the FAS who received any study drug; it is based on the treatment received (as treated). Treatment compliance/administration and all clinical safety variables will be analyzed using the SAF including patients randomized to fasinumab 1 mg Q4W, NSAIDs, and placebo.

Determination of 'as-treated' will be performed in the following stepwise manner:

- If a patient receives at least one dose of fasinumab, 'as treated' implies the patients data will be analyzed under the fasinumab arm.
- If a patient receives no doses of fasinumab and was ever dispensed NSAIDs, 'as treated' implies the patients' data will be analyzed under the NSAID arm.
- If a patient receives no doses of either fasinumab or NSAID, the patients data will be analyzed under the placebo arm.

Safety data from patients randomized to fasinumab 3 mg Q4W or 6 mg Q8W will not be included in the main safety analysis summaries, but will be summarized in separate tables.

### **3.5. The Urgent Safety Measure Set (USMS)**

The USMS will include all patients randomized to fasinumab 3 mg Q4W or 6 mg Q8W and is based on the treatment allocated (as randomized). The USMS will be utilized for all analyses of data collected from its included patients.

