### 3.2.2. Rationale for Dose Selection

Previous versions of this protocol randomized patients to receive fixed-dose, subcutaneous (SC) injections of 1 mg of fasinumab Q4W, 3 mg fasinumab Q4W, 6 mg fasinumab every 8 weeks (Q8W with alternating placebo injections at the monthly visits where fasinumab will not be given, to maintain the blind), celecoxib active comparator, diclofenac active comparator, or matching placebo. Based on April 2018 recommendations from an independent Data Monitoring Committee (DMC) that reviewed unblinded data from a different ongoing phase 3 study of fasinumab (R475-PN-1523), the decision was made to discontinue further evaluation of fasinumab at 3 mg Q4W or 6 mg Q8W in the phase 3 program. This recommendation was based on an imbalance in clinically relevant adverse events including time to total joint replacement, peripheral edema, arthralgia and a trend towards fractures. Under amendment 3 global, all patients previously randomized to 3 mg Q4W or 6 mg Q8W under an earlier version of the protocol were discontinued from study drug but encouraged to otherwise continue all protocol visits and study procedures in the follow-up period and the end of study phone call.

Clinical trial data, including PK data, that support selection of these fasinumab doses include those from the phase 1 studies in healthy volunteers (R475-PN-0817 and TDU-11480), the R475-PN-0901 phase 2 proof-of-concept study in patients with pain due to OA of the knee, the R475-PN-1227 phase 2/3 study in patients with OA of the hip or knee, and the R475-PN-0908 single-dose, proof-of-concept study in patients with sciatic pain.

Single SC doses of fasinumab of up to 30 mg were well-tolerated in healthy male and female subjects in the TDU-11480 study. All single IV doses of fasinumab in the R475-PN-0817 study in healthy male and female subjects were generally well tolerated at all but the highest IV dose (1 mg/kg). The occurrence of neurosensory AEs, which were transient and non-severe, led to the decision to refrain from escalating above the 1 mg/kg IV dose and instead, to expand enrollment of the 1 mg/kg IV cohort.

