#### 10.4.4. Safety Analysis

Safety data including TEAEs and treatment emergent AESIs, vital signs, physical examinations, laboratory tests, ECGs, and ADA formation will be listed and summarized by treatment group.

Thresholds for potentially clinically significant values in laboratory parameters and vital signs will be defined by the sponsor and be in effect at the time of final SAP approval.

The time interval to collect any AEs, including AESIs, is between the first dose of double-blinded study drug injection and the week 44 visit, as well as study drug-related SAEs occurring between the week 44 visit and the end of study.

For safety variables, 3 observation periods are defined:

- The pretreatment period is defined as the time from signing the ICF to before the first dose of study drug
- The treatment period is defined as the day of the first dose of study drug through to the day of the last dose of study drug (week 20) + 4 weeks.
- The follow-up period is defined as from the end of the on-treatment period (week 24) to the week 44 visit.

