##### 10.4.4.1. Adverse Events

###### Definitions

Treatment-emergent AEs are defined as those that are not present at baseline or represent the exacerbation of a pre-existing condition during the on-treatment period.

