###### Analysis

All AEs reported in this study will be coded using the currently available version of the Medical Dictionary for Regulatory Activities (MedDRA®). Coding will be to lowest level terms. The verbatim text, the preferred term (PT), and the primary system organ class (SOC) will be listed. The focus of AE reporting in the clinical study report will be on TEAEs. Post-treatment AEs and all AEs during the study will be summarized similarly as TEAEs.

Summaries of all TEAEs by treatment group will include:

- The number (n) and percentage (%) of patients with at least 1 TEAE by SOC and PT
- TEAEs by severity (according to the grading scale outlined in Section 9.5.1), presented by SOC and PT
- TEAEs by relationship to treatment (related, not related), presented by SOC and PT
- Treatment-emergent AESIs (defined with a PT or a pre-specified grouping)

Deaths and other SAEs will be listed and summarized by treatment group.

Treatment-emergent adverse events leading to permanent treatment discontinuation will be listed and summarized by treatment group.

In addition, AESIs will be reported according to the adjudicated diagnosis. Imaging data related to AA including change from baseline in joint space width will be summarized.

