## 5. STATISTICAL METHODS

For continuous variables, descriptive statistics will include the following: the number of patients reflected in the calculation (n), mean, median, standard deviation, minimum & maximum and 1st & 3rd quartiles (Q1 & Q3).

For categorical or ordinal data, frequencies and percentages will be displayed for each category.

**Period of Observation** - Unless otherwise stated, analysis of all safety and non-safety variables captured at multiple visits will be analyzed by the following observation periods:

- The Pre-Treatment Period is defined as the time from signing the ICF to before the first dose of study drug.
- The On-Treatment Period is defined as the time from the first dose of study drug up to 28 days after the last dose of study drug.
- The Follow-Up/Post-Treatment Period is defined from the end of the On-Treatment Period to the date of the follow-up clinic visit (Week 44 visit) or early termination date.

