### **Data from Urgent Safety Measure Patients**

Limited safety summaries will be presented based on the USM Analysis set including TEAEs and summaries of AAs, DAs and all joint replacements.

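### For the two fasinumab arms stopped for safety, the SAP specifies no table of ordinary adverse events beyond 28 days after the last dose

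*SAP*

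**What the plan says.** - **Population.** SAP 3.5 defines the USMS as all patients randomised to 3 mg Q4W or 6 mg Q8W and adds: "The USMS will be utilized for all analyses of data collected from its included patients". Protocol 6.1 puts these arms at about 60 patients each.
- **Planned safety output for them.** SAP 5.8.7, in its closing paragraph: "Limited safety summaries will be presented based on the USM Analysis set including TEAEs and summaries of AAs, DAs and all joint replacements".
- **What a TEAE is.** Protocol 10.4.4.1 limits TEAEs to events that are new or that "represent the exacerbation of a pre-existing condition during the on-treatment period". SAP 5 runs that period "from the first dose of study drug up to 28 days after the last dose of study drug". Protocol 10.4.4 likewise ends it at "the day of the last dose of study drug (week 20) + 4 weeks". Neither document gives a different window for the 8-week regimen.
- **Where later AEs are tabulated.** SAP 5.8.1 lists tables of post-treatment AEs and of all AEs on study. SAP 5.8 runs the safety analysis on the SAF. SAP 3.4 draws the SAF from the FAS, and SAP 3.1 removes these two arms from the FAS.
- **What the protocol promises.** AEs are recorded to week 44 (protocol 9.4.1). Protocol 10.4.4.1 says: "Post-treatment AEs and all AEs during the study will be summarized similarly as TEAEs". Protocol 10.3.2 says the safety data of these two arms go into separate tables, without limiting them to TEAEs.
- **Why the arms were stopped.** Protocol 3.2.2, where the trend at the cut-off end of the quote concerns fractures: "This recommendation was based on an imbalance in clinically relevant adverse events including time to total joint replacement, peripheral edema, arthralgia and a trend towards".

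**The concern.** Patients in the two stopped arms left dosing early and went straight into follow-up (protocol 7.1), so a large part of their AE observation comes after dosing ended. Of the events behind the stopping decision, joint replacement has its own summary. Arthralgia, peripheral oedema and fractures that are not adjudicated as AA do not: they are ordinary AEs. If they start more than 28 days after the last dose, no specified table counts them for these patients.

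At stake is complete safety reporting for the highest fasinumab doses given in this study. A reader of the report would see an AE table that stops four weeks after the last dose and could take it for the full AE experience of these patients. No efficacy test and no comparison for the 1 mg arm is affected.

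**Working it through.** **1. The plan's own figures reproduce.** Last dose at week 20 + 4 weeks = week 24, day 24 × 7 + 1 = 169. Week 24 + 20 weeks = week 44, day 44 × 7 + 1 = 309. Both match the schedule of events. Planned number: 600 + 300 + 300 + 300 = 1500, plus 2 × 60 = 120, gives 1620, as stated.

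**2. Coverage, by type of event.**

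| Event type | 1 mg, NSAID, placebo (SAF) | 3 mg Q4W, 6 mg Q8W (USMS) |
|---|---|---|
| AEs to 28 days after last dose | TEAE tables | TEAE summary |
| AEs after that, to week 44 | Post-treatment and all-AE tables | None specified |
| AA, DA, joint replacement | Planned | Planned, with no on-treatment limit stated |

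SAP 5.8.1 also lists a post-treatment AE listing, but makes no separate provision for the USMS.

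**3. Share of AE observation after the last dose that falls outside the TEAE window.** Inputs: window of 28 days (SAP 5); follow-up of 20 weeks = 140 days (protocol 5.1.5). The documents do not give the gap *d* between the last dose and the start of follow-up in these arms, so I take 0 to 28 days.

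Share = (d + 140 − 28) / (d + 140)

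- d = 0: 112 / 140 = 80%
- d = 28: 140 / 168 = 83%, that is, 20 of 24 weeks

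With complete follow-up of 120 patients this is between 120 × 16 = 1920 and 120 × 20 = 2400 patient-weeks.

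**4. Share of all time since first dose.** This depends on the number of injections *k*, which the documents do not give.

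- Follow-up starting 28 days after the last dose, 140 / (28k + 140): 83%, 71%, 63%, 56%, 50%, 45% for k = 1 to 6.
- Follow-up starting on the day of the last dose, 112 / (28(k − 1) + 140): 80%, 67%, 57%, 50%, 44% for k = 1 to 5.

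**5. The last 8-week interval in the 6 mg arm.** Active doses are 56 days apart, with a placebo injection at the 4-week visit between them (protocol 3.2.2). Study drug includes the oral capsules and matching placebo (protocol 7.1). Let *x* be the days from the last active injection to the last dose of any study drug.

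Share of the interval outside the window = max(0, 56 − (x + 28)) / 56

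- x = 0: 28 / 56 = 50%
- x = 14: 14 / 56 = 25%
- x = 28 (placebo injection given, or oral drug continued to then): 0%

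If the last dose means the last SC injection only, the result is 50% or 0%, according to whether the placebo injection was given.

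**The case against.** The best defence is that the list in SAP 5.8.7 is introduced by a word that need not close it. SAP 3.4 and protocol 10.3.2 also promise separate tables for these patients without confining them to TEAEs, and SAP 3.5 speaks of all analyses. On that view nothing has been ruled out. This stands in part: SAP 3.5 restricts nothing, and the restriction has to be read from SAP 5.8.7 together with the TEAE definition and the SAF. But SAP 5.8.7 calls the summaries limited and names what they contain, and the later-AE tables are tied to a set that excludes these patients. A programmer following the text would not produce them.

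It is also fair that the stopping signals came from another study (R475-PN-1523), that these are about 120 of 1620 patients on abandoned regimens, that the output is descriptive, and that AA, DA and joint replacements are covered. These facts limit the weight of the point but leave the gap.

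Four stronger readings are tempting, and the documents do not carry them:

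- *Half of the 8-week interval is lost in the 6 mg arm.* That is only the upper bound. The loss falls to zero if a placebo injection or oral study drug followed four weeks after the last active dose.
- *Most of these patients' total time on study is uncounted.* The number of injections is not given, and at 5 or 6 injections the share is at or below one half.
- *There is nothing to compare these arms with.* The SAF tables report the other arms, though over the whole enrolment period.
- *The SAP made an undeclared departure.* SAP 1.2.4 declares the USMS, and protocol 10.3.2 had already moved these arms to tables it did not specify. Whether a narrower AE scope needed its own entry is arguable.

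**Conclusion.** The point holds as a gap in the specified safety output. For the 3 mg Q4W and 6 mg Q8W patients, SAP 5.8.7 names no table of ordinary AEs after the 28-day window. Those AEs are collected to week 44, protocol 10.4.4.1 says post-treatment and all AEs will be summarised, and SAP 3.5 reads more broadly.

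The firm figure is 80% to 83% of planned AE observation after the last dose. It assumes that follow-up starts 0 to 28 days after the last dose and is completed. For 6 mg Q8W, between 0% and 50% of the last dosing interval is also outside the window.

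It cannot be said that the stopped arms will show low AE counts; that would depend on when events occurred. The change should be made, since these arms were closed over events of this kind, but it does not touch the primary result.

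**What to change.** In the SAP 5.8.7 paragraph on urgent safety measure patients, add for the USMS, by randomised arm:

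- all AEs on study, by SOC and PT, from first dose to week 44 or early termination;
- post-treatment AEs, by SOC and PT, to the same end point;
- the observation time per arm beside each table, because these patients were stopped at different times.

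Then reconcile SAP 5.8.7 with SAP 3.5 and protocol 10.4.4.1, so that all three give the same AE scope for these arms.

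I would not ask for a 56-day on-treatment window for the 6 mg arm. It would create an arm-specific TEAE definition, and the all-AE table makes it largely redundant. Nor would I require a concurrent comparator: patients stopped early, set beside controls planned for about 308 days without adjustment for observation time, could themselves appear to have fewer AEs.

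The cost is a few extra descriptive tables. Both table types are already planned for the SAF, and no new data are needed.
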